Stroke is the leading cause of disability and death among adults in China, with an annual death toll of approximately 1.5 million and a disability rate of about 75%. About 70% of stroke patients suffer from ischemic stroke, and the recurrence rates at 3 months, 6 months, and 12 months after the first ischemic stroke are approximately 10.9%, 13.4%, and 14.7%, respectively. The risk of death and disability after the recurrence of ischemic stroke is 9.4 times that of the initial stroke. This project increases the sample size based on the existing ischemic stroke follow-up cohort and conducts a 1-year follow-up to observe the recurrence situation, mRs scores, and adverse events after discharge. Combining complex multi-dimensional data such as demographic data, physical examination, medical history, imaging images, medication information, scale scores, CYP2C19 genotype test results, laboratory examinations, etc.; using convolutional neural networks for lesion segmentation of ischemic stroke patient imaging and feature extraction; using Cox regression models to obtain factors influencing recurrence and adverse events; constructing an ischemic stroke recurrence risk prediction model within 1, 3, 6, and 12 months using the XGBoost combined with convolutional neural network algorithm (Convolutional Neural Network, CNN). Exploring the predictive effect of XGBoost on ischemic stroke recurrence risk at different times and providing new ideas and methods for the prevention and control of major chronic diseases.

3. Design Type: Cohort Study.

4. Research Subjects: Inpatients with ischemic stroke from the Department of Neurology at the Second Affiliated Hospital of Nanchang University and more than ten tertiary hospitals in the province.

5. Sample Size: 2400 cases.

6. Inclusion Criteria:

(1) Inclusion criteria:

1) Aged 18-85; 2) Diagnosed with ischemic stroke or transient ischemic attack (diagnosis in line with the standards set by the Cerebrovascular Disease Group of the Neurology Society of the Chinese Medical Association in 2014); 3) Within the acute phase of onset (2 weeks); 4) Voluntarily participate and sign an informed consent form.

(2) Exclusion criteria:

1) Patients with cancer; 2) Patients with cardiogenic infarction, other causes of cerebral infarction, or stroke of unknown cause; 3) Patients with hemorrhagic stroke, mixed stroke, and tumor stroke; 4) Patients with severe heart, lung, or liver system diseases; 5) Patients judged by researchers to have poor compliance and unable to complete long-term follow-up; 6) Patients currently participating in any clinical trial of investigational drugs or medical devices.

7. Observation Indicators:

Demographic data, physical examination, medical history, imaging images, medication information, scale scores, CYP2C19 gene test results, laboratory examinations, etc., mRS scores, recurrence situation (whether recurrent, number of recurrences, time of recurrence, type of stroke recurrence, etc.), and adverse events (type of adverse event, severity, start time, stop time, etc.) of ischemic stroke patients within 1, 3, 6, and 12 months after discharge.

8. Statistical Analysis Methods:

This study uses SPSS25.0 software for statistical analysis. Measurement data that conforms to the normal distribution are expressed as mean \pm standard deviation (); Measurement data that do not conform to the normal distribution are expressed as median (quartile) [M(Q1, Q3)]; Count data are expressed as frequency and percentage (%). The comparison between count data groups uses the chi-square test or Fisher's exact probability method; the comparison between measurement data groups uses the t-test or Mann-Whitney U test. $P < 0.05$ is considered statistically significant.

9. Modeling Methods:

CNN, Logistic, SVM, RF, XGBoost model construction is implemented using PyCharm (professional v2018.3) software under the Anaconda Python3.6 environment. Data preprocessing uses the numpy (1.20) and Pandas (1.2.0) packages, CNN image processing model construction uses the tensorflow (2.1.1) architecture, data analysis and model construction use Scikit-learn (0.23.1).

Brain imaging feature extraction: Introducing deep convolutional neural network models such as UNet++, FCN, AlexNet, etc., to process brain imaging images, while considering the natural 3D attributes of brain imaging images, using 3D convolution, pooling to capture changes in brain imaging between continuous slices; comparing the effects of different deep convolutional neural network models, selecting the optimal model as the method for extracting brain imaging features.

Prediction model construction: The variables screened by Cox regression with statistical differences are fused with the imaging features extracted by CNN. The fused data is divided into training sets, validation sets, and test sets, using a ten-fold cross-validation training method, respectively establishing machine learning-based ischemic stroke recurrence risk prediction models (research models: XGBoost; control models: Logistic, SVM, RF) within 1, 3, 6, and 12 months after discharge, continuously optimizing the model effects on the validation set until the optimal.

Model Evaluation: After the model effect reaches the ideal effect, compare the performance evaluation indicators of the research model and the control model on the test set (AUC value, sensitivity, time efficiency, etc.). AUC, sensitivity, and time efficiency are used to evaluate the comprehensive predictive ability, accuracy rate, and prediction efficiency of the model, respectively.

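### In the order written, predictors are chosen with the test patients' recurrence outcomes before the data are split, so test-set AUC and sensitivity would be too high

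*Combined protocol and SAP*

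**What the plan says.** The opening summary plans "using Cox regression models to obtain factors influencing recurrence and adverse events", and then prediction models for recurrence within 1, 3, 6 and 12 months.

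Section 9 (Prediction model construction) gives the sequence in two consecutive sentences: "The variables screened by Cox regression with statistical differences are fused with the imaging features extracted by CNN. The fused data is divided" into training, validation and test sets, with ten-fold cross-validation. What is divided is a dataset that already holds only the screened variables.

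The only significance threshold in the plan is in Section 8, where P < 0.05 "is considered statistically significant". That section does not name Cox regression, so applying the threshold to the screen is an inference.

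Under Model Evaluation, the plan will "compare the performance evaluation indicators of the research model and the control model on the test set", using AUC, sensitivity and time efficiency. It describes no external cohort.

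**The concern.** A test set gives an honest estimate only if its outcomes played no part in building the model. Here the screen uses recurrence, the outcome later predicted, and it precedes the split.

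The mechanism is simple. A variable with no real effect passes a whole-cohort screen mostly when its chance association points the same way in the later training and test patients. The model learns that direction from the training patients, and the test patients then appear to confirm it. New patients would not.

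Test-set AUC and sensitivity are the plan's measures of how well recurrence is predicted, and these figures would be overstated. The list of Cox factors, a separate aim, does not rest on the test set and is unaffected.

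**Working it through.** The plan gives no target AUC, effect size or derivation of its sample size, so it has no figure to reproduce. Direction and size were checked by simulation.

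**Inputs from the plan**
- 2400 patients (Section 5).
- Threshold P < 0.05 (Section 8), taken as two-sided and applied to the Cox screen.
- Recurrence of 14.7% at 12 months and 10.9% at 3 months (opening summary). These are background rates after a first ischemic stroke, and using them for this cohort is an assumption. They imply 2400 × 0.147 = 353 and 2400 × 0.109 = 262 events.

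**Assumptions not in the plan**
- A 20% test set: 480 test patients and 1920 for fitting, with no separate validation set.
- 20 to 200 independent, normally distributed candidates.
- Five true predictors with log hazard ratio 0.32 per SD (best possible AUC 0.70).
- Exponential event times, censored at the end of the window.

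**Steps.** Screen each candidate by a univariable Cox score test on all 2400 patients. Fit a logistic model (one of the plan's control models) on the 1920. Compute AUC in the 480 test patients and in 20,000 new patients.

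Optimism = AUC(test) − AUC(new), for the same fitted model.

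Expected noise variables retained = 0.05 × (candidates − 5). For 100 candidates this is 0.05 × 95 = 4.75.

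**Results** (300 replicates, simulation SE about 0.002; differences taken before rounding)

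| Candidates | Expected noise variables | Test AUC, 14.7% | New-patient AUC, 14.7% | Optimism, 14.7% | Optimism, 10.9% |
|---|---|---|---|---|---|
| 20 | 0.75 | 0.703 | 0.699 | +0.004 | +0.007 |
| 50 | 2.25 | 0.703 | 0.695 | +0.007 | +0.011 |
| 100 | 4.75 | 0.711 | 0.689 | +0.023 | +0.028 |
| 200 | 9.75 | 0.720 | 0.678 | +0.042 | +0.055 |

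Repeat runs of the 14.7% setting gave +0.007 to +0.015 for 50 candidates, +0.021 to +0.028 for 100 and +0.035 to +0.042 for 200.

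**Is the order the cause?** With the screen restricted to training patients, optimism stayed within 0.003 of zero in these settings, and within 0.006 in the repeat runs and the weaker-signal runs below.

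**Sensitivity** (14.7%, cut-off at 80% training specificity), test against new patients: 0.47 and 0.46 for 50 candidates, 0.49 and 0.45 for 100, 0.50 and 0.44 for 200.

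**Other assumptions**
- Weaker signal (log hazard ratio 0.25, 14.7%): +0.007, +0.019 and +0.028 for 30, 50 and 100 candidates. At 10.9%: +0.015, +0.018 and +0.033, and up to +0.066 for 200.
- No true predictor (extreme case, 14.7%): test AUC 0.527, 0.549, 0.570 and 0.597 for 20, 50, 100 and 200 candidates, where the truth is 0.500.
- A 10% or 30% test set, 200 candidates: +0.042 or +0.041.
- A 5% event rate, assumed because the plan gives no 1-month rate: +0.03 to +0.11 for 50 to 200 candidates if the screen uses that window's events. It would be less if one 12-month screen served all windows.

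**Other model types** (100 replicates, SE about 0.003 to 0.004; 200 candidates, five true predictors), test against new patients: logistic 0.715 and 0.677, XGBoost 0.690 and 0.657, random forest 0.684 and 0.654, SVM 0.672 and 0.637. XGBoost minus logistic was −0.025 on the test set and −0.020 in new patients, a shift of 0.005. With no true predictor the shift was 0.024 to 0.029. True effects were linear, and no CNN was simulated.

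**The case against.** **The leak is inferred.** The plan never says that all 2400 patients are screened, and a short methods paragraph may simply list the data before the split. It is true that the leak follows from the written order and not from an explicit statement, so the conclusion is conditional on following that order. But the plan divides the already fused data, and no other sentence restores an untouched test set.

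**Independent candidates flatter the size.** Laboratory, scale and history variables are likely to be correlated. With assumed blocks of five at correlation 0.5, optimism was about zero at 50 or fewer candidates and +0.004 to +0.050 at 100 to 200, depending on event rate and signal strength. This stands: it reduces the size but does not reverse the direction.

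**The bias is small against noise.** Test-set AUC varied between replicates with an SD of about 0.03, so at 20 to 50 candidates the optimism is a fraction of the sampling error. This also stands. But sampling error has no preferred direction, whereas this bias pushes upward and a confidence interval around the reported AUC would not reveal it.

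**The planned model comparison barely moves.** Correct when real signal exists. The harm is to the absolute figures.

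**Repeating the screen within folds is not needed for the test set.** Correct: training-only screening without it already removed the test-set bias. Repetition protects the cross-validated results used for tuning.

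**The CNN step.** Section 9 describes "comparing the effects of different deep convolutional neural network models, selecting the optimal model as the method for extracting brain imaging features" without saying on which patients or by what criterion. The summary gives the task as "using convolutional neural networks for lesion segmentation of ischemic stroke patient imaging and feature extraction", so this would bias recurrence performance mainly if the network were trained or chosen on recurrence, which the plan does not say. It is a clarification, not part of the finding.

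**Conclusion.** The concern holds. Followed as written, the plan lets the recurrence outcomes of test patients influence predictor selection, which is a wrong order of analysis and not merely missing detail. The upward direction for AUC and sensitivity is well established.

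The size cannot be fixed from the documents because the number of candidates, their correlation, the test share and the sensitivity cut-off are not stated. As an illustration, with real signal and the plan's 10.9% to 14.7% rates, the excess AUC is negligible with about 20 candidates. It is roughly 0.02 to 0.05 with 100 to 200 independent candidates, less if they are correlated, and somewhat more if predictors are weak or events few. It should be corrected before the analysis, because a test set whose outcomes have shaped the predictors cannot be made fully independent afterwards.

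**What to change.** Reorder Section 9 (Prediction model construction), for example: *Patients are first divided into a development set (training and validation) and a test set, which is locked. Cox screening and model tuning use the development set only; in ten-fold cross-validation the screen is repeated inside each fold. The final pipeline is frozen and applied once to the test set.*

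Two clarifications fit in the same paragraph: the number of candidate variables, and that the CNN extractor is trained and chosen on non-test patients by a stated criterion such as segmentation accuracy.

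The cost is one rewritten paragraph, reordered code, some computing for the repeated screen, and CNN training on somewhat fewer patients. The CNN need not be retrained in each fold. The reported AUC may be somewhat lower. No extra patients or data are needed.

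### The Cox screen is placed before the data split, so test-set outcomes help choose the predictors that the test set then evaluates

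*Combined protocol and SAP*

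**What the plan says.** Section 9, Prediction model construction, gives the sequence in two consecutive sentences. First: "The variables screened by Cox regression with statistical differences are fused with the imaging features extracted by CNN". Then: "The fused data is divided into training sets, validation sets, and test sets, using a ten-fold cross-validation training method". What is divided has therefore already been screened. Under Model Evaluation, the plan will "compare the performance evaluation indicators of the research model and the control model on the test set", by AUC, sensitivity and time efficiency.

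The opening summary presents Cox regression as an aim for the whole cohort, "using Cox regression models to obtain factors influencing recurrence and adverse events". Nothing there or in section 9 confines the screen to training patients or repeats it within the ten folds.

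Section 8 sets a general significance level of P < 0.05 but does not list Cox regression among its methods. The plan does not give the number of candidate variables, whether the Cox fit is univariable or multivariable, how continuous variables are coded, or which endpoint and horizon drive the selection.

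**The concern.** A test set gives a fair estimate of performance only if its outcomes played no part in building the model. Choosing variables by their association with the outcome is part of building the model. If the Cox screen uses all 2400 patients, a noise variable that happens to track recurrence among the test patients is more likely to be kept, and it then earns credit on those patients. Cross-validation applied after the screen does not undo this, because every fold inherits the same selected list.

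At stake are the AUC and sensitivity reported for all four models at each of the four horizons. Once the test outcomes have been used for selection, that test set cannot be made clean again, so the order of steps has to be settled before modelling starts.

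**Working it through.** **No figure to reproduce.** The plan states no AUC and gives 2400 without a derivation. The size of the effect can only be simulated, under stated assumptions.

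**Inputs from the plan.** N = 2400. The summary says that "recurrence rates at 3 months, 6 months, and 12 months after the first ischemic stroke are approximately 10.9%, 13.4%, and 14.7" per cent. Expected events are N x rate:
- 3 months: 2400 x 0.109 = 262
- 6 months: 2400 x 0.134 = 322
- 12 months: 2400 x 0.147 = 353

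These rates refer to first ischaemic stroke, while section 6 also admits TIA ("Diagnosed with ischemic stroke or transient ischemic attack"). No 1-month rate is given.

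**Assumptions.** An 80/20 split (1920 training, 480 test, with 480 x 0.147 = 71 test events at 12 months); 40 or 100 clinical candidates; four true effects of log-HR 0.25 per SD, or none; ten unscreened imaging features, two of them informative.

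**Method.** A candidate is kept if its univariable Cox score test has P < 0.05. The model is fitted on the 1920 training patients in both arms; only the data used for the screen differ.

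Difference = test AUC (screen on all 2400) - test AUC (screen on the 1920)

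**Independent candidates, 12 months, 300-400 cohorts per setting** (differences were taken before rounding):

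| Candidates | True clinical effects | Logistic, all / training | Difference | XGBoost, all / training | Difference |
|---|---|---|---|---|---|
| 40 | 4 | 0.672 / 0.660 | +0.011 | 0.650 / 0.641 | +0.009 |
| 100 | 4 | 0.679 / 0.652 | +0.027 | 0.656 / 0.634 | +0.021 |
| 40 | none | 0.604 / 0.584 | +0.020 | 0.581 / 0.565 | +0.016 |
| 100 | none | 0.616 / 0.574 | +0.042 | 0.592 / 0.561 | +0.032 |

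Separate re-runs of the Logistic case with four true effects gave +0.011 (40 candidates) and +0.025 to +0.028 (100). A different design, with eight true effects of log-HR 0.3, 30 candidates and no imaging features, gave only +0.005.

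**How much of the difference is bias.** In 6000 new patients, the Logistic model screened on all data had AUC 0.662 (40 candidates) and 0.655 (100). The optimism of its own test set is therefore 0.672 - 0.662 = 0.010 and 0.679 - 0.655 = 0.024. The small remainder arises because a screen on more patients chooses slightly better variables.

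**Correlated candidates** (Logistic, univariable screen, four true effects):

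| Within-block correlation | Block size | 40 candidates | 100 candidates |
|---|---|---|---|
| 0.3 | 5 | +0.008 | +0.021 |
| 0.5 | 5 | +0.001 | +0.014 |
| 0.5 | 10 | -0.010 | +0.001 |

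A multivariable screen stayed positive under correlation, at +0.011 to +0.028. The new-patient check was run for independent candidates only. The negative entry is thus a difference from the training-only screen, not a measured bias.

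**Effect on the model comparison.** Screening before the split moved the XGBoost-minus-Logistic gap by -0.002 (40 candidates) and -0.006 (100) with true effects present. This used fixed XGBoost settings and unpenalised Logistic; SVM was not simulated. For scale, the standard error of the paired AUC difference on 480 test patients was about 0.020, so the 95% interval is about ±1.96 x 0.020 = ±0.04.

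**The case against.** The strongest reply is that the plan never says outright that test patients enter the screen; the authors may intend a training-only screen and have compressed the description. That is possible, and one sentence would settle it. But the written order is screen, fuse, divide, and the whole-cohort Cox aim in the summary points the same way.

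A second reply is that the size is unknown and may be trivial. This stands in part. Laboratory values, scale scores and medical history are unlikely to be independent, and with correlation 0.5 and a univariable screen the difference could vanish or turn slightly negative. The standard error of a single AUC of 0.66 on 71 events is about 0.037 (Hanley-McNeil), larger than most of the differences above. Sampling error, however, shrinks with more data and is visible in an interval; selection on test outcomes is neither.

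Three stronger readings are tempting, and the documents do not support them:

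- **The screening threshold is missing.** The general P < 0.05 in section 8 is the evident threshold, even though that section does not name Cox regression. What is missing is the form of the Cox model and the candidate list.
- **The XGBoost comparison is invalid.** All four models share the screened set, so the leak is largely common to them and the gap moves little.
- **A null XGBoost-versus-Logistic result would be uninterpretable because the screen removes non-linear signal.** The plan sets no hypothesis test or margin and describes its aim as "Exploring the predictive effect of XGBoost on ischemic stroke recurrence risk at different times". Any comparison applies to the inputs used. A linear main-effect screen can drop a trendless U-shaped predictor (it passed in 7-9% of simulated cohorts, against 47-92% with quartile coding). Yet moving from a training-only screen to the full candidate list changed the gap materially in only one of four scenarios: from -0.019 to +0.010, with two strong trendless U-shapes. In the other three it moved by 0.008 or less.

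**Conclusion.** The concern holds as a fault in the order of steps. Followed as written, the plan lets test-set outcomes influence which predictors are evaluated on the test set, so the reported AUC and sensitivity are not a clean estimate of performance. That conclusion rests on the text alone.

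The size does not. The bias is usually upward, but a reader might infer certain inflation of a known amount, and the documents do not support that: candidate number, correlation, signal strength and split are all unstated. The figures of about 0.01 and 0.025 hold only under the independent-candidate assumptions shown. The change should be made before modelling, but it does not call the cohort or the choice of models into question.

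**What to change.** 1. Divide the data first. Run the Cox screen on training data only and repeat it inside each training fold, so that no validation or test outcome is used in selection.
2. Keep the whole-cohort Cox analysis solely for the separate aim of describing influencing factors.
3. State the terms of the screen: candidate list, univariable or multivariable fit, coding, endpoint and horizon, and that P < 0.05 applies to it.
4. Report the XGBoost-minus-control AUC difference with a 95% confidence interval from one clearly defined evaluation: either the untouched test set, or out-of-fold predictions with the screen nested in each fold. The two should not be mixed. Pooled out-of-fold predictions on all 353 expected 12-month events include the test patients; an untouched 20% test set leaves about 353 - 71 = 282 events for development.
5. Optional: a sensitivity comparison of the four models on the unscreened baseline list plus imaging features, because a linear main-effect screen can miss predictors that act only through curvature or interaction.

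Items 1 to 4 cost plan wording, a different order of steps and repeated screening, with no new data; reported AUCs may be somewhat lower. Item 5 roughly doubles the model fits and is not a general gain in prediction: in three of the four scenarios the full list lowered the XGBoost AUC, by 0.002 to 0.011 at 12 months.

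### Predictors are screened on recurrence before the data are divided, and the four models are then compared with no paired interval and no account of hospital

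*Combined protocol and SAP*

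**What the plan says.** In the combined protocol and SAP, section 9 (Modeling Methods), the paragraph on prediction model construction gives this order of work.

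- Selection and fusion come first: "The variables screened by Cox regression with statistical differences are fused with the imaging features extracted by CNN".
- The split follows: "The fused data is divided into training sets, validation sets, and test sets, using a ten-fold cross-validation training method".
- Tuning is open-ended: "continuously optimizing the model effects on the validation set until the optimal".
- The paragraph on model evaluation then says to "compare the performance evaluation indicators of the research model and the control model on the test set", using AUC, sensitivity and time efficiency.

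The imaging paragraph of section 9 describes "comparing the effects of different deep convolutional neural network models, selecting the optimal model as the method for extracting brain imaging features" and does not say which patients or which target decide the choice. Section 4 recruits from one named hospital and "more than ten tertiary hospitals in the province". Hospital is not mentioned in the split, the models or the evaluation. Section 9 gives no split proportions and no interval for a difference between models. The group-comparison tests in section 8 (t, Mann-Whitney, chi-square, Fisher) do not cover AUCs of models scored on the same patients.

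**The concern.** The opening summary gives the aim as "Exploring the predictive effect of XGBoost on ischemic stroke recurrence risk at different times", and the comparison with logistic regression, SVM and random forest is how section 9 judges it. Three weaknesses bear on that comparison.

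1. **Leakage.** If Cox screening uses all patients, the recurrences of the test patients have already influenced which variables enter the models. The test AUC is then not an out-of-sample figure, and it tends to be too high.
2. **Uncertainty not shown.** Three controls at four horizons make 12 AUC contrasts, each reported as a bare difference. A reader could not tell a real ranking from a chance one. Patients within a hospital may also resemble one another, so an interval that ignores hospital could be too narrow.
3. **Possible waste of information.** If the test set is one hold-out, most recurrences play no part in the comparison, although ten folds could give every patient an out-of-sample prediction.

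**Working it through.** **Inputs from the plan.** 2400 patients (section 5). Background recurrence of 10.9%, 13.4% and 14.7% at 3, 6 and 12 months (opening summary); no 1-month rate is given. The plan reports no precision or power figure to reproduce.

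**Assumptions.** Test share 20%, AUC 0.70, correlation ρ between the two AUC estimates 0.6-0.8, 12 hospitals, no loss to follow-up. Event counts are approximate: the background rates run from a first stroke, while the models run from discharge and TIA is eligible.

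**Step 1: leakage.** Simulate 2400 patients with 14.7% events by 12 months and predictors that are pure noise. Screen each by Cox regression at p<0.05, fit a model on 80% and score the other 20%. On average 5% of the candidates pass by chance.

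| Candidates | Expected to pass | Test AUC, screened before split | Test AUC, screened inside training |
|---|---|---|---|
| 50 | 2.5 | about 0.55 | 0.50 |
| 100 | 5 | about 0.57 | 0.50 |
| 200 | 10 | about 0.60 | 0.50 |

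The true AUC is 0.50 throughout, so the excess comes entirely from the order of steps.

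**Step 2: events.** All patients: 2400 × 0.109 = 262 at 3 months and 2400 × 0.147 = 353 at 12 months. In a 20% test set (480 patients): 52 and 71.

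**Step 3: precision at 12 months, independent patients.** Hanley-McNeil, with n1 events and n0 non-events:

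SE² = [A(1−A) + (n1−1)(B−A²) + (n0−1)(C−A²)] / (n1·n0), where B = A/(2−A) and C = 2A²/(1+A).

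For A = 0.70, B = 0.5385 and C = 0.5765. With n1 = 70.6 and n0 = 409.4, SE = 0.03669. With n1 = 352.8 and n0 = 2047.2, SE = 0.01640.

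95% half-width of a paired difference = 1.96 × SE × √(2(1−ρ)):

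- 20% hold-out: 0.064 (ρ = 0.6) to 0.045 (ρ = 0.8)
- all patients: 0.029 to 0.020

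The ratio is 0.03669/0.01640 = 2.2. In 500 simulated cohorts with two models actually fitted (20 predictors, no imaging, no Cox screening) it was 0.0228/0.0113 = 2.0. No test of an AUC difference is planned, so power serves only as a gauge of information. For 0.70 against 0.75 it is 34-59% on the hold-out and 94% or more with all patients.

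**Step 4: if the true difference varies between hospitals.** Variance = τ²·Σw² + 2(1−ρ)·SE², where w is each hospital's share of patients. In the worst case tried, τ = 0.05 and the lead hospital holds half, so Σw² = 0.25 + 11 × (0.5/11)² = 0.2727 and τ²·Σw² = 0.00068.

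| | SD, 20% hold-out | SD, all patients | Ratio | Power for 0.05, all patients |
|---|---|---|---|---|
| ρ = 0.6 | 0.0419 | 0.0299 | 1.4 | 39% |
| ρ = 0.8 | 0.0349 | 0.0281 | 1.2 | 43% |

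The hold-out power in this case is 22-30%.

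**Step 5: can hospital-level AUCs come from random folds?** With 12 equal hospitals and ten random folds, a hospital-by-fold cell holds 2400/12/10 = 20 patients, hence 20 × 0.109 = 2.2 events at 3 months and 20 × 0.147 = 2.9 at 12 months. An AUC in such a cell is unstable or undefined. Within-fold AUC from random folds therefore cannot feed a hospital-by-hospital combination.

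**The case against.** **The text may already intend rotation.** The split sentence speaks of test sets in the plural and of ten folds. A reader might infer from the later singular that one hold-out is certain and the 2.2-fold gain assured. The documents do not settle this. If the folds already rotate the test set, the precision gain disappears, while the order of screening, the missing interval and the missing hospital remain.

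**The order of sentences may not be the order of computation.** Screening might be meant inside training. The plan does not say so; it describes the fused data as what is divided.

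**Repeating the networks is expensive and may be pointless.** The opening summary gives the CNNs the task of lesion segmentation and feature extraction. If they are trained and chosen on lesion masks alone, reselecting them in every fold removes little outcome leakage. This stands and limits the remedy.

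**A protected test set has merits.** It evaluates one frozen model, whereas out-of-fold results describe a modelling procedure. That is a fair reason to hesitate in an exploratory cohort, and it is a cost of the change.

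**More patients may not settle the comparison.** This also stands: in the worst case of step 4, using everyone still gives only 39-43% power for a difference of 0.05.

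**Conclusion.** As written, the plan lets test outcomes influence the choice of predictors, and the reported AUCs will tend to be too high. The figures 0.55-0.60 against 0.50 show the mechanism with noise predictors. They do not estimate the bias in this study, which depends on the number of candidates and their real signal. A reader might also infer that leakage, or mixing hospitals across the split, favours XGBoost over the controls; nothing in the documents shows that.

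The lack of a paired interval and of any account of hospital holds on either reading of the split. The precision gain is conditional. At 12 months it is 2.2-fold against a single 20% hold-out with no hospital variation, 1.2 to 1.4-fold in the worst case tried, and none if the folds already rotate. It rests on an assumed AUC, correlation, test share and hospital structure. The correction is worth making before modelling starts.

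**What to change.** 1. Divide the data first. Repeat Cox screening, tuning and any CNN step that uses recurrence inside each training fold, by a procedure fixed in advance in place of open-ended optimisation. A CNN trained and chosen only on lesion masks need not be reselected in each fold; state which case applies.
2. State how the ten folds relate to the test set. If it is a single hold-out, use the ten folds as outer folds and compare the four models on out-of-fold predictions for all patients with known status at each horizon.
3. Report every AUC difference with a paired 95% interval that allows for hospital, using one consistent scheme:
   - random folds, AUC computed within fold and combined, with a hospital-level bootstrap of the combined difference; coverage with about 12 hospitals has not been checked and should be; or
   - folds formed by hospital, with hospital-level differences combined by Hartung-Knapp and very small hospitals merged. A simulation with 12 hospitals but no fold structure gave coverage of 0.935-0.995, so the full procedure is not yet validated.

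   Do not mix the two schemes.

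**Cost.** No extra patients or data. Computing rises: ten Cox screenings and inner tuning and, only if the networks use recurrence, at least 3 × 10 = 30 CNN trainings instead of 3. Other downsides are the loss of a locked test set, results that describe a procedure and not one frozen model, few clusters, and probably a lower reported AUC. If one hospital holds half the patients and folds follow hospitals, that hospital is predicted from only the other half of the cohort.
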